### List of Abbreviations

ADR	Adverse Drug Reaction
AE	Adverse Event
ALT	Alanine Aminotransferase
AST	Aspartate Aminotransferase
CIMP	CpG Island Methylator Phenotype
CMS	Consensus Molecular Subtype
CRF	Case Report Form
CR	Complete Response
CTCAE	Common Terminology Criteria for Adverse Events
ctDNA	Circulating Tumor DNA
DFS	Disease-Free Survival
DLT	Dose Limiting Toxicity
EKG	Electrocardiogram
ECOG	Eastern Cooperative Oncology Group
GCP	Good Clinical Practice
Hgb	Hemoglobin
IB	Investigator's Brochure
ICH	International Conference on Harmonization
iCPD	Immune Confirmed Progressive Disease
IEC	Independent Ethics Committee
IHC	Immunohistochemistry
IMP	Investigational Medicinal Product
INR	International Normalized Ratio
IRB	Institutional Review Board
ITT	Intention To Treat
iUPD	Immune Unconfirmed Progressive Disease
IV	Intravenous
IVRS	Interactive Voice Response System
LA	Locally advanced
mCRC	Metastatic Colorectal Cancer

MoA	Mechanism of Action
MSI	Microsatellite Instability
MSI-L	Microsatellite Instability – Low
MSI-H	Microsatellite Instability - High
MSS	Microsatellite Stable
NCI	National Cancer Institute
NFkB	Nuclear Factor Kappa Light Chain Enhanced of Activated B cells
NK	Natural Killer
OS	Overall Survival
ORR	Objective Response Rate
PCR	Polymerase Chain Reaction
PD	Progressive Disease
PD-1	Programmed Death - 1
PD-L1	Programmed Death Ligand 1
PDx	Pharmacodynamics
PGx	Pharmacogenetics/Pharmacogenomics
PFS	Progression Free Survival
РК	Pharmacokinetics
РО	Per Os
PR	Partial Response
PS	Performance Status
RECIST	Response Evaluation Criteria in Solid Tumors
ROS	Reactive oxygen species
RR	Response Rate
SAE	Serious Adverse Event
SBRT	Stereotactic Body Radiation Therapy
Treg	T-regulatory
TGF-β	Transforming Growth Factor $\beta$
WBC	White Blood Cell
ULN	Upper Limit of Normal
UR	Unresectable

### Table 1: Schedule of Assessments (Cohort A-C)

Test		Су	cle 1	Cycle 2		Cycle 3 (and all subsequent cycles)		End-of- Treatment	28-day follow up after progression	Long term follow up
Measure	Day -28 to treatment	Day 1	Day 15	Day 1	Day 15	Day 1	Day 15	Day of dis- continuation or within 7 days after		Every 3 months after 28 day follow up
Inclusion/exclusion criteria	х	Х								
Demographic data	X									
Medical history	X									
Cancer disease history	X									
Prior anticancer drug/ radiotherapy/ procedures	х									
Concurrent medications	X									
Written informed consent	X									
Enrollment (if eligible) a	X									

Test		Cycle 1		Cycle 2		Cycle 3  and all subsequent cycles)		End of Treatment	28day follow-up after progression	Long- term follow-up
Measure	Day -28 to treatment	Day 1	Day 15	Day 1	Day 15	Day 1	Day 15	Day of discontinuati on or within 7 days after		Every 3 months after 28- day follow up
Physical examination b,p	Х	X	X	Х	x	x	Х	x	X	
Vital signs including weight p and height (latest height on record acceptable; height is only performed at screening)	X	Х	х	Х	x	х	x	Х	Х	Х
ECOG PS p	Х	Х	X	х	Х	х	Х	Х	Х	Х
Toxicity assessment p	х	Х	Х	х	х	Х	х	x	x	Xr
12-lead EKG c,d, p	Х				x				X	
Full serum chemistry e, p	Х	Х	X	Х	Х	Х	Х	X	Х	
Complete blood count e,	Х	Х	Х	х	х	Х	х	Х	х	
Free T4, TSH e, f, p	X					X			X	
ANA, RF e,	Х								X	
Urinalysis (dipstick) e, p	Х	X		Х		Х		X	X	

β-HCG pregnancy test, FSH e, f,p	х	Х		х		х			Xº	
Test		Cycle 1		Cycle 2		Cycle 3  and all subsequent cycles)		End of treatment	28 day follow up after progression	Long- term follow-up
Measure	Day -28 to treatment	Day 1	Day 15	Day 1	Day 15	Day 1	Day 15	Day of discontinuati on or within 7 days after		Every 3 months after 28- day follow up
HIV, HBV, HCV testing	Х									
Documentation of AEs, concomitant medications, and procedures q	Х	Х	Х	Х	Х	Х	Х	Xq	Xq	Х
M7824 Administration p		Xt	X t	Х	х	x	х			
Patient-reported outcomes p		х	х	Х	Х	Х	Х		Х	
Tumor biopsy g,p	Х			Х					Х	
MSI testing h	Х									
Tumor evaluation by imaging (w/collection of available staging imaging prior to study enrollment) 1,j,p	х					Х			X u	Xq

Verification of available specimen for mutation profiling k	Х									
Test		Cycle 1		Cycle 2		Cycle 3 subsequent o	6  and all cycles)	End of Treatment	28 day follow up after progression	Long- term follow- up r
Measure	Day -28 to treatment	Day 1	Day 15	Day 1	Day 15	Day 1	Day 15	Day of discontinuati on or within 7 days after		Every 3 months after 28- day follow up
Verification of available specimen for TGFβ 1,2,3 analysis p	Х	х		х	х	Xs			Х	
Blood biomarkers (including circulating cytokines) 1,p	х	х		х	х	х			Х	
Collection of buccal and fecal swabs for microbiome testing p	х			х		Xs		Х		
Verification of available specimen for PD-L1 expression m	х			х						
Collection of specimens for analysis of pharmacokinetics of M7824 n,p		х	X	Х				X		

aEnrollment will be done after the confirmation of fulfilling all screening inclusion criteria without matching any exclusion criterion. bPhysical examination should include a dermatological examination. If abnormal skin findings are observed, patient should be

referred to a dermatologist for biopsy of suspicious lesions. An ophthalmology examination including slit lamp evaluation inclusive of the anterior segment and with visual acuity should be conducted at Screening. At subsequent visits, eye signs and symptoms should be checked. If there are any clinically relevant findings then an appropriate ophthalmology examination including slit lamp evaluation inclusive of the anterior segment and with visual acuity should be obtained within 2 days. Starting with C1D15, a focused examination may be performed centered around patient's symptoms at an assigned visit.

°12-lead EKG should be performed as soon after completion of infusion as possible.

dEKGs are to be performed every 6 weeks.

eLaboratory draws may be performed up to 72 hours before a scheduled treatment.

fFor women of child-bearing potential. FSH should be drawn if clarification of post-menopausal state is warranted. Refer to Appendix 2 for further details.

gMandatory fresh tumor biopsies will be collected prior to treatment and prior to dose 3. An optional tumor biopsy following progression may be offered to the patient.

hPerformed on archival tissue or fresh biopsy. MSI testing performed in a CLIA certified laboratory is acceptable and does not need to be repeated (see section 6.4.5)

iTumor measurements should occur with CT imaging or MRI. Ideally the same methodology would be used over the course of the study for a given patient. Bone scan should be done at screening if clinically indicated. For collection of those prior imaging studies prior to informed consent, readily available imaging studies since the onset of metastatic/unresectable disease are to be prioritized for collection. If the results of a CT scan or MRI performed within 4 weeks prior to first treatment are available, the screening CT and/or MRI does not need to be performed.

jTumor measurements are to be assessed every 8 weeks (+/- 5 days). For subjects continuing treatment beyond 12 months, tumor evaluations should take place every 12 weeks (+/- 5 days).

kTo be performed on archival tissue or fresh biopsy either via hotspot next general sequencing panel in CLIA certified molecular diagnostics laboratory at MD Anderson.

Plasma will be sent for markers including, but not limited to, interleukin (IL) IL-1 $\alpha$ , IL-1 $\beta$ , IL-2, IL-5, IL-6, IL-8, IL-13, TNF- $\alpha$ , MCP, MIP-1 $\beta$ , G-CSF, GM-CSF, IFN- $\gamma$  via a cytokine assay ((Meso Scale Discovery (MSD), 40 Plex). Leukocyte subpopulations and immune activation status will be assessed by flow cytometry (fluorescence-activated cell sorter [FACS]) on PBMC from heparinized blood samples (10 mL, tubes). Additional time points to include for collection after cycle 3, day 1 include C4D1, C5D1, and C6D1. No additional biomarker samples for this analysis will be collected while the patient is receiving treatment on study.

mPD-L1 expression by immunohistochemistry on fresh biopsy. Repeat IHC on FRESH biopsy prior to dose 3 of M7824 nOne 10 mL vial of blood will be drawn prior to M7824 infusion and immediately following completion of M7824 infusion for doses 1 and 3 (cycle 1 day 1 and cycle 2 day 1) for analysis of pharmacokinetics. One 10 mL vial of blood will be drawn prior to M7824 infusion of M7824 infusion for doses 2 (cycle 1 day 15) and dose 6/end of treatment (whichever comes first). Refer to Section 6.4.3 for details on processing of PK samples.

°β-hCG (no FSH) at post-progression follow-up visit

pWindow of +/- 7 days is allowed

qAdverse events are recorded and assessed continuously throughout the trial (see Section 6.4.1.3) and are assessed for final outcome at the End of Treatment visit. After the End of Treatment visit only AEs that are deemed attributable to trial drug by the Investigator should be documented until the Safety Follow-up visit.

rFor up to one year following discontinuation of treatment on study.

sCycle 3, Day 1 collection only.

tPatients must remain at the CTRC for two hours of observation following the first two doses of therapy.

uOnly to be performed if no disease progression was documented previously.

 Table 2: Schedule of Assessments (Cohort B)
 Particular

Test		Сус	le 1	Сус	ele 2	Cycle 3 (and all subsequent cycles)		End-of- Treatment	28 day follow up after progression	Long term follow up
Measure	Day -28 to treatment	Day 1	Day 15	Day 1	Day 15	Day 1	Day 15	Day of dis- continuation or within 7 days after		Every 3 months after 28 day follow up
Inclusion/exclusion criteria	Х	Х								
Demographic data	Х									
Medical history	Х									
Cancer disease history	Х									
Prior anticancer drug/ radiotherapy/ procedures	х									
Concurrent medications	Х									
Written informed consent	Х									
Enrollment (if eligible) a	X									

Test		Cyc	le 1	Cyo	ele 2	Cycle 3  and all subsequent cycles)		End of Treatment	28 day follow-up after progression	Long- term follow-up
Measure	Day -28 to treatment	Day 1	Day 15	Day 1	Day 15	Day 1	Day 15	Day of discontinuati on or within 7 days after		Every 3 months after 28- day follow up
Physical examination b,q	Х	Х	Х	х	Х	х	Х	Х	Х	
Vital signs including weight and height (latest height on record acceptable) q	х	Х	Х	х	Х	Х	Х	Х	Х	Х
ECOG PSq	Х	X	х	Х	Х	x	Х	x	x	X
Toxicity assessment q	х	X	x	х	Х	x	Х	Xs	Xs	Х
12-lead EKG c,d, q	Х				Х				X	
Full serum chemistry e, q	Х	Х	X	х	Х	x	Х	X	Х	
Complete blood count e, 9	Х	Х	Х	Х	Х	Х	Х	х	Х	
Free T4, TSH e, f, q	х					X			Х	
ANA, RF e,	Х								Х	
Urinalysis (dipstick) e, q	X	X		X		X		X	X	
β-HCG pregnancy test, FSH e, f,q	X	x		x		X			X p	

Test		Cycle 1		Cycle 2	Cycle 3  and all subsequent cycles)		End of treatment	28 day follow up after progression	Long- term follow-up	
Measure	Day -28 to treatment	Day 1	Day 15	Day 1	Day 15	Day 1	Day 15	Day of discontinuati on or within 7 days after		Every 3 months after 28- day follow up
HIV, HBV, HCV testing	Х									
Documentation of AEs, concomitant medications, and procedures q	х	Х	Х	х	х	X	Х	X r	Xr	Х
M7824 Administration q		X u	X u	х	х	Х	х			
SBRT Administration w			Х							
Patient-reported outcomes q		Х	х	х	х	х	Х		х	
Tumor collection g,q	х		X x	Х					х	
MSI testing h	Х									
Confirmation of CMS status i	х									

Test		Cycle 1		Cycle 2	2 Cycle 3  and all subsequent cycles)		End of Treatment	28 day follow up after progression	Long- term follow-up s	
Measure	Day -28 to treatment	Day 1	Day 15	Day 1	Day 15	Day 1	Day 15	Day of discontinuati on or within 7 days after		Every 3 months after 28- day follow up
Verification of available specimen for analysis of TGFβ 1,2,3 q	Х	Х		х	х	X t			Х	
Tumor evaluation by imaging (w/collection of available staging imaging prior to study enrollment) j,k,q	х					х			X v	X r
Verification of available specimen for mutation profiling 	х									
Blood biomarkers (including circulating cytokines) m,q	х	Х		Х	х	х			Х	
Collection of buccal and fecal swabs for microbiome testing q	х			x		X t		X		
Verification of available specimen for PD-L1 expression n	х			Х						

Collection of samples	Х	Х	Х		Х	
for pharmacokinetics of						
M7824 o,q						

aEnrollment will be done after the confirmation of fulfilling all screening inclusion criteria without matching any exclusion criterion. bPhysical examination should include a dermatological examination. If abnormal skin findings are observed, patient should be referred to a dermatologist for biopsy of suspicious lesions. An ophthalmology examination including slit lamp evaluation inclusive of the anterior segment and with visual acuity should be conducted at Screening. At subsequent visits, eye signs and symptoms should be checked. If there are any clinically relevant findings then an appropriate ophthalmology examination including slit lamp evaluation inclusive of the anterior segment and with visual acuity should be obtained within 2 weeks, unless an urgent necessity is determined by the treating provider that requires a sooner evaluation. Starting with C1D15, a focused examination may be performed centered around patient's symptoms at an assigned visit.

°12-lead EKG should be performed as soon after completion of infusion as possible.

dEKGs are to be performed every 6 weeks.

eLaboratory draws may be performed up to 72 hours before a scheduled treatment.

fFor women of child-bearing potential. FSH should be drawn if clarification of post-menopausal state is warranted. Refer to Appendix 2 for further details.

gMandatory fresh tumor biopsies will be collected prior to treatment and prior to dose 2 (i.e., on cycle 1, day 15) and prior to dose 3. An optional tumor biopsy following progression may be offered to the patient.

hMSI testing performed in a CLIA certified laboratory is acceptable and does not need to be repeated (see section 6.4.5)

iCMS on FFPE at CLIA testing laboratory on archival primary tissue or fresh biopsy.

jTumor measurements should occur with CT imaging or MRI. Ideally the same methodology would be used over the course of the study for a given patient. Bone scan should be done at screening if clinically indicated. For collection of those prior imaging studies prior to informed consent, readily available imaging studies since the onset of metastatic/unresectable disease are to be prioritized for collection. If the results of a CT scan or MRI performed within 4 weeks prior to first treatment are available, the screening CT and/or MRI does not need to be performed.

kTumor measurements are to be assessed every 8 weeks (+/- 5 days). For subjects continuing treatment beyond 12 months, tumor evaluations should take place every 12 weeks (+/- 5 days).

To be performed on archival tissue or fresh biopsy either via hotspot next general sequencing panel in CLIA certified molecular diagnostics laboratory at MD Anderson.

mPlasma will be sent for markers including, but not limited to, interleukin (IL) IL-1α, IL-1β, IL-2, IL-5, IL-6, IL-8, IL-13, TNF-α, MCP, MIP-1β, G-CSF, GM-CSF, IFN-γ via a cytokine assay ((Meso Scale Discovery (MSD), 40 Plex). Leukocyte subpopulations and immune activation status will be assessed by flow cytometry (fluorescence-activated cell sorter [FACS]) on PBMC from heparinized blood samples (10 mL, tubes). Additional time points to include for collection after cycle 3, day 1 include C4D1, C5D1, and C6D1. No additional biomarker samples for this analysis will be collected while the patient is receiving treatment on study. nPD-L1 expression by immunohistochemistry on fresh biopsy. Repeat IHC on FRESH biopsy prior to dose 3 of M7824 oOne 10 mL vial of blood will be drawn prior to M7824 infusion and immediately following completion of M7824 infusion for doses 1 and 3 (cycle 1 day 1 and cycle 2 day 1) for analysis of pharmacokinetics. One 10 mL vial of blood will be drawn prior to M7824 infusion for doses 2 (cycle 1 day 15) and dose 6/end of treatment (whichever comes first). Refer to Section 6.4.3 for details on processing of PK samples.

pβ-hCG (no FSH) at post-progression follow-up visit

qWindow of +/- 7 days is allowed

rAdverse events are recorded and assessed continuously throughout the trial (see Section 6.4.1.3) and are assessed for final outcome at the End of Treatment visit. After the End of Treatment visit only AEs that are deemed attributable to trial drug by the Investigator should be documented until the Safety Follow-up visit.

sFor up to one year following discontinuation of treatment on study.

tCycle 3, Day 1 collection only.

uPatients must remain at the CTRC for two hours of observation following the first two doses of therapy.

vOnly to be performed if no disease progression was documented previously.

wSBRT administration (total 24 Gy over 3 consecutive business days at a daily fraction of 8Gy to start within 7 days following cycle 1, day 15 and completed prior to cycle 2, day 1). While SBRT is preferred, Intensity-modulated radiation therapy (IMRT) or 3D conformal techniques may be utilized at the discretion of the treating radiation oncologist depending on the dose to surrounding normal tissues. Patient will receive a total dose of 24Gy over three days with one of the following modalities, at the discretion of the treating radiation oncologist: SBRT, IMRT and 3D conformal.

xBiopsy to be performed cycle 1, day 15

\_\_\_\_\_

Test		Cyc	le 1	Су	cle 2	Сус	le 3	Cycle 4 x subsequer	(and all nt cycles)	End of treatment	Long folla	g term ow up
Measure	Day -28 to treatmen t	Day 1	Day 15	Day 1	Day 15	Day 1	Day 15	Day 1	Day 15	Day of dis- continuation or within 7 days after	28 day follow up after progr ession	Every 3 months after 28 day follow up
Inclusion/exclusion criteria	Х	Х										
Demographic data	X											
Cancer disease history	Х											
Prior anticancer drug/ radiotherapy/ procedures	Х											
Medical history	х											
Concurrent medications	Х											

#### Table 3: Schedule of Assessments (Cohort D)

Vital signs including weight q and height (latest height on record acceptable; height is only performed at screening)	x	х		x	х	х	x	х	Х	х	X	Х
Test		Сус	le 1	Су	cle 2	Сус	le 3	Cycle 4 x subsequer	(and all nt cycles)	End of treatment	Long follo	g term ow up
Measure	Day -28 to treatmen t	Day 1	Day 15	Day 1	Day 15	Day 1	Day 15	Day 1	Day 15	Day of dis- continuation or within 7 days after	28 day follow up after progr ession	Every 3 months after 28 day follow up
Written informed consent	Х											
Enrollment (if eligible) a	Х											
Physical examination b,q	Х	Х	х	х	X	х	х	Х	Х	Х	Х	
ECOG PSq	х	Х	Х	Х	Х	Х	Х	х	X	X	Х	

Toxicity assessment q	Х	х	х	Х	х	х	х	Х	Х	Xs	Xs	
Test		Сус	le 1	Су	cle 2	Сус	ele 3	Cycle 4 y subsequer	(and all nt cycles)	End of treatment	Long	g term ow up
Measure	Day -28 to treatmen t	Day 1	Day 15	Day 1	Day 15	Day 1	Day 15	Day 1	Day 15	Day of dis- continuation or within 7 days after	28 day follow up after progr ession	Every 3 months after 28 day follow up
Documentation of AEs, concomitant medications, and procedures q	х	Х	Х	Х	Х	Х	Х	Х	х	Х	х	Xs
12-lead EKG c,d, q	Х			х			х				х	х
Full serum chemistry e, q	Х	X	Х	X	X	X	X	X	Х	Х		
Complete blood count e,	Х	х	х	Х	Х	х	х	Х	Х	Х		
Free T4, TSH e, f, q	х							Х				
ANA, RF e,	х											
Urinalysis (dipstick) e, q	X	х	х			x		X		Х		

β-HCG pregnancy test, FSH e, t,q	Х	Х	Х			Х		Х				
HIV, HBV, HCV testing	Х											
Test		Cyc	le 1	Су	cle 2	Сус	le 3	Cycle 4 x subsequent	(and all cycles)	End of treatment	Long term follow up	
Measure	Day -28 to treatmen t	Day 1	Day 15	Day 1	Day 15	Day 1	Day 15	Day 1	Day 15	Day of dis- continuation or within 7 days after	28 day follow up after progr ession	Every 3 months after 28 day follow up
M7824 Administration		X u	X u	Х	х	Х	Х	Х	Х			
Tumor biopsy g											X n	
Patient-reported outcomes q		Х	х	Х	Х	х	Х	Х	Х		Х	
MSI testing h	Х											
Verification of available specimen for mutation profiling m	х											
Tumor evaluation by imaging (w/collection of available staging	х							х			X v	Xs

imaging prior to study enrollment) j,k,q												
Verification of available specimen for TGFβ 1,2,3 q	х	х		х	х	Х	Х	X t			Х	
Test		Cyc	le 1	Су	rcle 2	Сус	le 3	Cycle 4 x subsequer	(and all nt cycles)	End of treatment	Long follo	g term w up
Measure	Day -28 to treatmen t	Day 1	Day 15	Day 1	Day 15	Day 1	Day 15	Day 1	Day 15	Day of dis- continuation or within 7 days after	28 day follow up after progr ession	Every 3 months after 28 day follow up
Verification of available specimen for PD-L1 expression n	х											
Collection of buccal and fecal swabs for microbiome testing q	х			Х		х		х				
Verification of available specimen for testing of pharmacokinetics of M7824 o.q		х	х	х		х				х		
Blood for collection of ctDNA	х							Ху		Х		

aEnrollment will be done after the confirmation of fulfilling all screening inclusion criteria without matching any exclusion criterion. bPhysical examination should include a dermatological examination. If abnormal skin findings are observed, patient should be referred to a dermatologist for biopsy of suspicious lesions. An ophthalmology examination including slit lamp evaluation inclusive of the anterior segment and with visual acuity should be conducted at Screening. At subsequent visits, eye signs and symptoms should be checked. If there are any clinically relevant findings then an appropriate ophthalmology examination including slit lamp evaluation inclusive of the anterior segment and with visual acuity should be obtained within 2 days. Starting with C1D15, a focused examination may be performed centered around patient's symptoms at an assigned visit.

°12-lead EKGs should be performed as soon after completion of infusion as possible.

dEKGs are to be performed every 6 weeks.

eLaboratory draws may be performed +/- 7 days of a scheduled treatment.

fFor women of child-bearing potential. FSH should be drawn if clarification of post-menopausal state is warranted. Refer to Appendix 2 for further details.

gAn optional tumor biopsy following progression may be offered to the patient.

hPerformed on archival tissue or fresh biopsy. MSI testing performed in a CLIA-certified laboratory is acceptable and does not need to be repeated (see section 6.4.5)

iBlood for ctDNA collection to be drawn after14 days of completion of standard treatment.

jTumor measurements should occur with CT imaging or MRI. Ideally the same methodology would be used over the course of the study for a given patient. Bone scan should be done at screening if clinically indicated. For collection of those prior imaging studies prior to informed consent, readily available imaging studies since the onset of metastatic/unresectable disease are to be prioritized for collection. If the results of a CT scan or MRI performed within 4 weeks prior to first treatment are available, the screening CT and/or MRI does not need to be performed.

kTumor measurements are to be assessed every 12 weeks (+/- 5 days). For subjects continuing treatment beyond 12 months, tumor evaluations should take place every 12 weeks (+/- 5 days).

To be performed on archival tissue or fresh biopsy either via hotspot next general sequencing panel in CLIA certified molecular diagnostics laboratory at MD Anderson. TGFβR2, ACVR2A, SMAD2 and SMAD4 will need to be performed if not done previously. mPlasma will be sent for markers including, but not limited to, interleukin (IL) IL-1α, IL-1β, IL-2, IL-5, IL-6, IL-8, IL-13, TNF-α, MCP, MIP-1β, G-CSF, GM-CSF, IFN-γ via a cytokine assay ((Meso Scale Discovery (MSD), 40 Plex). Leukocyte subpopulations and

immune activation status will be assessed by flow cytometry (fluorescence-activated cell sorter [FACS]) on PBMC from heparinized blood samples (10 mL, tubes).

nPD-L1 expression by immunohistochemistry on archival tumor specimen or fresh tumor tissue (if available).

oOne 10 mL vial of blood will be drawn prior to M7824 infusion and immediately following completion of M7824 infusion for doses 1 and 3 (cycle 1 day 1 and cycle 2 day 1) for analysis of pharmacokinetics. One 10 mL vial of blood will be drawn prior to M7824 infusion of M7824 infusion for doses 2 (cycle 1 day 15) and dose 6/end of treatment (whichever comes first). Refer to Section 6.4.3 for details on processing of PK samples.

pβ-hCG (no FSH) at post-progression follow-up visit

qWindow of +/- 7 days is allowed

rAdverse events are recorded and assessed continuously throughout the trial (see Section 6.4.1.3) and are assessed for final outcome at the End of Treatment visit. After the End of Treatment visit only AEs that are deemed attributable to trial drug by the Investigator should be documented until the Safety Follow-up visit.

sFor up to one year following discontinuation of treatment on study.

tCycle 4, Day 1 collection only.

uPatients must remain at the CTRC for two hours of observation following the first two doses of therapy.

vOnly to be performed if no disease progression was documented previously.

"Including confirmation of R0 resection of metastatic disease

xAt the discretion of the treating provider and patient in the absence of recurrence or progression

yCycle 4 Day 1, and every 12 weeks (+/1 14 days) thereafter as long as the patient continues study treatment.

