#### 6.1.1 Screening and Baseline Procedures and Assessments

There is a 28-day washout / recovery period for prior anticancer treatment (for example, cytoreductive therapy, radiotherapy [with the exception of palliative radiotherapy delivered in a normal organ-spearing technique], immune therapy, or cytokine therapy except for erythropoietin) and major surgery before the start of trial treatment (Section 4.3.2). Hematology and chemistry laboratory samples must be drawn and reviewed within 72 hours prior to dose administration.

During the screening period and before any trial related investigations and assessments are started, the subjects will be asked to sign the relevant ICFs. The subjects' information that will be documented during screening includes the demographic information (birth date, sex, ethnicity, and race) and the complete medical history, including the history of the tumor disease and prior anticancer therapies, previous medications (prior 30 days to signing of ICF), concomitant medications, and baseline medical condition (the information of concomitant medications and AEs will be monitored throughout the trial treatment period).

During screening, subjects will undergo a complete physical examination, dermatological assessments (assessments for skin lesions or rash with biopsy of suspicious lesions), recording

vital signs, including body weight and height (height only at screening), 12-lead electrocardiogram (EKG), and a determination of the ECOG PS (Appendix 1). The screening laboratory examination includes hematology, full serum chemistry and full urinalysis. Antinuclear antibody (ANAs), rheumatoid factor (RF), free thyroxine (T4), and TSH will also be assessed at screening.

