### 6.1.2 Treatment period

For this protocol, a cycle is defined as 28 days. M7824 will be given until confirmed progression, unacceptable toxicity, or any criterion for withdrawal from the trial or IMP occurs (see Section 4.5). Subjects who have experienced a PR or CR should continue treatment through the end of 12 months, although additional treatment is possible. If the Investigator believes that a subject may benefit from treatment beyond 12 months, it may be permissible after discussion with the principal investigator. In the case of PD, subjects should continue treatment through their next tumor assessment, if they meet the criteria described in Section 4.5.1.

For subjects who achieve a PR or CR on M7824 therapy and then subsequently develop disease progression after stopping therapy, but prior to the end of the trial, a re-initiation course of treatment at the same dose and schedule and treatment duration up to 12 months is allowed at the discretion of the Investigator and agreement of the trial principal investigator. In order to be eligible for retreatment, the subject must not have experienced any toxicity that led to treatment discontinuation of the initial M7824 therapy. Prior to re-initiation of the study treatment, malignant

disease needs to be radiologically re-staged to assess all known sites of the disease and to establish a new baseline for subsequent tumor measurements. Relevant safety laboratory samples must be drawn and results available and verified prior to re-initiating of treatment.

Subjects will be asked to visit the investigational site according to the Schedules of Assessments (see **Tables 1-3**). In addition, the tumor evaluation (see Section 6.3) has a tumor assessment visiting time window of 5 days prior to dosing (-5 days). Furthermore, if any Screening procedures are conducted within 3 days prior to Day 1 of trial treatment (Cycle 1, Day 1), the assessments scheduled on Cycle 1, Day 1 do not need to be repeated except for the evaluation of AEs and concomitant medications.

During the treatment period, the following assessments will be performed (see **Tables 1-3** for the detailed schedule):

- AEs and concomitant medications will be documented in each study visit
- ECOG PS will be assessed prior to trial treatment on Day 1 (unless the Screening ECOG PS was performed within 3 days prior to Day 1)

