- Physical examination will be performed prior to trial treatment on Day 1 (Cycle 1) and then prior to trial treatment according to **Tables 1-3**
- Eye signs and symptoms should be checked. If clinically relevant findings then an appropriate ophthalmology examination including slit lamp evaluation inclusive of the anterior segment and with visual acuity should be obtained within 2 days
- Dermatological assessments (assessments for skin lesions or rash with biopsy of suspicious lesions according to **Tables 1-3**)
- Vital signs, including body weight, will be assessed prior to trial treatment according to **Tables 1-3**.
- The 12-lead EKG will be assessed according to **Tables 1-3**.
- The laboratory hematology tests will be assessed prior to trial treatment according to **Tables 1-3**. Complete blood count results must be drawn and reviewed within 72 hours prior to dose administration.
- Full serum chemistry will be assessed prior to trial treatment according to **Tables 1-3**. Samples for full chemistry results must be drawn and reviewed within 72 hours prior to dose administration.
- A basic urinalysis will be performed prior to trial treatment every according to Tables 1-3.
- Samples for ANAs and RF according to **Tables 1-3**.

- A serum HCG pregnancy test will be required at Screening, urine or serum β-HCG pregnancy test will be performed prior to each administration of the study drug (if applicable).
- The tumor evaluation (see Section 6.3) will be performed prior to treatment at week 8, and then once every 8 weeks, with a tumor assessment visiting time window of 5 days prior to dosing. For subjects continuing treatment beyond 12 months (in consultation with the principal investigator), tumor evaluations should take place every 12 weeks.
- Tumor biopsies at Week 4, prior to the third treatment dose (-7 day window permitted). Archival tissue may be used in place of a fresh pretreatment biopsy if adequate tumor is available for analysis. If insufficient tissue is available for analysis for pretreatment tumor, then a mandatory fresh biopsy must be obtained. In cohort A, the site of tumor tissue for the pretreatment sample, whether archival or fresh, may be from the primary tumor or the metastasis. In cohort B, the site of tumor for the pretreatment sample, in order to classify the CMS subtype, must come from the primary tumor. The week 4, on-treatment biopsy for both cohorts may come from the primary tumor or from a metastatic site.

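### Table 3 footnote e lets Cohort D CBC and chemistry be drawn up to 7 days before or after a scheduled treatment, against the body-text rule of 72 hours before the dose

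*Combined protocol and SAP*

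**What the plan says.** Footnote e of Table 3 (Cohort D) reads "Laboratory draws may be performed +/- 7 days of a scheduled treatment". It is attached to the row "Full serum chemistry" and to the CBC row. Both rows are marked at screening, at every Day 1 and Day 15 dosing visit, and at End of Treatment. The chemistry row also carries footnote q, a general visit window of 7 days either way.

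The body text sets a different limit:

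- Section 6.1.1: "Hematology and chemistry laboratory samples must be drawn and reviewed within 72 hours prior to dose administration".
- Section 6.1.2, CBC: "Complete blood count results must be drawn and reviewed within 72 hours prior to dose administration". A parallel sentence covers chemistry.
- Section 6.4.3 repeats the 72-hour limit for both tests before each dose. It adds that relevant results have to be obtained and checked before M7824 is given.

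Footnote e of Table 1 (Cohort A-C) agrees with the body text: "Laboratory draws may be performed up to 72 hours before a scheduled treatment". Footnote e of Table 2 (Cohort B) has the same wording.

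**The concern.** A CBC or chemistry result informs a dose only if it is recent and known before the infusion starts. The Cohort D footnote, taken literally, accepts a sample that is 4 to 7 days old, or one drawn after the infusion it was meant to inform.

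The results bear on dosing. Section 5.5.3.4 treats anemia as a potential risk of M7824, requires hemoglobin every 2 weeks before treatment, and describes a work-up when it falls below 8 g/dL. Section 4.1.4.2 requires permanent discontinuation if a drug-related Grade 3 or higher amylase or lipase abnormality without pancreatitis has not resolved within two doses. Both tests belong to the chemistry panel, although Table 7 requires them only on Day 1 of each cycle, so that example does not reach the Day 15 doses.

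Staff who schedule visits work from the tables, and Section 6.1.2 sends them there. Site practice could therefore follow the looser text and produce either dosing on an out-of-date sample or avoidable protocol deviations.

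**Working it through.** This is a comparison of texts. There is no planned figure to reproduce, and the only arithmetic is a conversion of units.

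**1. Do both texts cover the same tests?** Yes. Footnote e of Table 3 sits on the CBC and chemistry rows, and Sections 6.1.1, 6.1.2 and 6.4.3 name hematology (or CBC) and chemistry.

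**2. Do both cover Cohort D?** Yes. The Section 6.1.2 bullets begin "The laboratory hematology tests will be assessed prior to trial treatment according to" and "Full serum chemistry will be assessed prior to trial treatment according to", each followed by a reference to Tables 1-3, and Table 3 is the Cohort D schedule. None of the three sections makes an exception for that cohort.

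**3. How do the limits compare, for a dose given on its scheduled day?**

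| | Earliest draw | Latest draw |
|---|---|---|
| Table 3 footnote e | 7 × 24 = 168 h before | 168 h after |
| Sections 6.1.1, 6.1.2, 6.4.3 | 72 h before | before the dose |

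The footnote opens 168 − 72 = 96 h (4 days) too early, and everything it allows after the dose is outside the rule.

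**4. Is a 3-day limit used elsewhere?** Yes. For Cycle 1 Day 1, Section 6.1.2 waives repeat assessments (except adverse events and concomitant medications) only "if any Screening procedures are conducted within 3 days prior to Day 1 of trial treatment (Cycle 1, Day 1"). A limit of about 72 hours is thus the consistent intention.

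**5. Is the reference point the same?** No. Footnote e in all three tables counts from the scheduled treatment, while the body text counts from dose administration. Section 4.1.1.3 lets Cohort D doses move by up to 7 days. A sample taken 3 days before the scheduled date, for an infusion then given 4 days late, is 3 + 4 = 7 days old. Copying the Table 1 wording into Table 3 would not close that gap, so the corrected note should count from the actual dose.

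**6. What about the general 7-day window?** It is footnote p in Table 1 and q in Tables 2 and 3, and it also appears on the chemistry rows of Tables 1 and 2. Those tables still state 72 hours through footnote e. In Table 3 no footnote does.

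**7. Which other tests carry footnote e in Table 3?** Free T4/TSH, ANA/RF, urinalysis and the pregnancy test. The 72-hour limit is stated for none of them. For the pregnancy test, Section 6.1.2 requires testing before each administration and Section 6.4.4 wants the latest result available before the next dosing. Only a draw after the dose conflicts with these.

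**The case against.** The strongest reply is that the rule is already in place. The footnote is permissive and the body text is mandatory, and it is stated in three sections. Staff sent to the tables by Section 6.1.2 meet the 72-hour sentence in the same bullet. This stands, and it is why the point is minor. It does not remove the conflict: the documents have no clause saying which text prevails, and Table 3 states a permission that the body text denies.

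A second reply is that the footnote only lets laboratory work move with the visit. It speaks of a scheduled treatment, Cohort D doses have the same 7-day window, and in Tables 1 and 2 a visit window and a 72-hour limit stand side by side on the chemistry row. The reading is reasonable, and may be what was meant, but the footnote does not say it. For a dose given on schedule the footnote still admits a late or stale sample.

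A third reply is that the limit was relaxed on purpose for Cohort D. No text says so, and if it were true, Sections 6.1.1, 6.1.2 and 6.4.3 would need an exception, so an edit is due either way.

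A reader might also infer that Cohort D lacks a pre-dose safety check, or that a large share of its doses will be given on invalid samples. The documents support neither. The check is required by the body text, and nothing shows when samples will be drawn. The width of a permitted window is not a frequency of use.

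**Conclusion.** The contradiction is real and can be shown from the protocol alone. For CBC and chemistry in Cohort D, Table 3 footnote e is wrong as written. It is a patient-safety point of minor severity, because the correct rule already stands in Sections 6.1.1, 6.1.2 and 6.4.3.

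For a dose on its scheduled day, its size is 96 hours of excess before the dose and up to 168 hours after it. How many doses would be affected cannot be known from the documents. The conclusion assumes that the footnote letters on the CBC and chemistry rows were extracted correctly. The content of the note, which is about laboratory draws, and its place on the laboratory rows of all three tables support that.

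No effect on the toxicity stopping rule, the ctDNA endpoint, the sample size or any analysis follows from this.

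**What to change.** - In Table 3, for CBC and full serum chemistry at dosing visits, reword footnote e to: up to 72 hours before dose administration, counted from the actual dose.
- In Tables 1-3, add that the general 7-day visit window (p in Table 1, q in Tables 2 and 3) does not override the 72-hour limit at dosing visits. This works whether or not that letter is attached to a given CBC row, which the extracted text leaves unclear. Do not strike the letter from whole rows, because it also governs visits without a dose.
- Leave the timing of End-of-Treatment and follow-up laboratory tests, free T4/TSH, ANA/RF and urinalysis unchanged.
- State that any on-treatment pregnancy test, serum or urine, is done before the dose, in line with Sections 6.1.2 and 6.4.4.

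The cost is low: one reworded footnote and two clarifying sentences, which can go into the next amendment. Sample size, endpoints and analyses do not change.
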